11.7 Secondary Efficacy Analysis: Oxygenation

11.7.1 PaO₂ and PaO₂/FiO₂

Continuous data descriptive statistics (3.1) for PaO₂ and PaO₂/FiO₂, change from baseline, percentage of change from baseline in accordance to 3.2 will be reported for each treatment arm at all scheduled visits. T-test assuming unequal variance p-values and 95% CI comparing the differences between SOC and treatment arms A and B will also be provided for percentage change from baseline analysis.

11.7.2 Time to first return to SpO₂ > 94% on room air

The time first return to SpO₂ on room air (Day) is defined as:

Date of first return to SpO₂>94% on room air – Date of Baseline Assessment + 1.

If the patient did not experience a return of SpO₂>94% on room air the patient will be censored at the last known date the patient is known to not have achieved this criterion:

Final Date of Confirmation of no return to SpO₂>94% on room air - Date of Baseline Assessment + 1.

If a patient died before achieving a return of SpO₂>94% on room air, the patient will be censored as a competing risk based on the following:

Date of Death - Date of Baseline Assessment + 1.

11.7.3 Time to first return to PaO₂ of 80-100 mmHg.

The time first return to PaO₂ of 80-100 mmHg is defined as:

Date of first return to PaO₂ of 80-100 mmHg – Date of Baseline Assessment + 1.

If the patient did not experience a return to PaO₂ of 80-100 mmHg the patient will be censored at the last known date the patient is known to not have achieved this criterion:

Final Date of Confirmation of no return to PaO₂ of 80-100 mmHg - Date of Baseline Assessment + 1.

If a patient died before achieving a return to PaO₂ of 80-100 mmHg, the patient will be censored as a competing risk based on the following:

Date of Death - Date of Baseline Assessment + 1.

11.7.4 Time to first return to PaO₂/FiO₂ of > 400 mmHg.

The time first return to PaO₂/FiO₂ of > 400 mmHg is defined as:

Date of first return to PaO₂/FiO₂ of > 400 mmHg – Date of Baseline Assessment + 1.

If the patient did not experience a return to PaO₂/FiO₂ of > 400 mmHg the patient will be censored at the last known date the patient is known to not have achieved this criterion:

Final Date of Confirmation of no return to PaO₂/FiO₂ of > 400 mmHg - Date of Baseline Assessment + 1.

If a patient died before achieving a return to PaO₂/FiO₂ of > 400 mmHg, the patient will be censored as a competing risk based on the following:

Date of Death - Date of Baseline Assessment + 1.

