**Figure 1 Putative Mechanism of Ifenprodil on Glutamate Signaling in Neutrophils and T cells**

[figure not shown]
ALI is a direct and indirect injury to alveolar epithelial cells and capillary endothelial cell, causing diffuse pulmonary interstitial and alveolar edema and acute hypoxic respiration failure ([Zhe et. al., 2018](#)). ALI is characterized by reduced lung volume and compliance, and imbalance of the ventilation/perfusion ratio, inducing hypoxemia and respiratory distress and its severe stage (oxygen index <200) known as acute respiratory distress syndrome (ARDS). ARDS is a common, devastating clinical syndrome of acute lung injury with high mortality ranging from 40% to 60%. Furthermore, pathological findings show that 64% of ARDS patients may have pulmonary fibrosis (PF) during convalescence ([Qiao et. al., 2009](#)).

Antagonism of glutamate signaling could therefore ameliorate some of the complications of ALI and thereby also prevent the development of PF.

A recent paper from an independent group in China, found that repurposing ifenprodil could be useful for preventing virus-induced acute lung injury ([Zhang et. al., 2019](#)). A genome wide RNA interference (RNAi) screen was performed to identify gene targets that could rescue lung cell viability from H5N1 infection *in vitro*. Drug bank searches for compounds that could affect the same gene targets as were identified by the RNAi screen selected ifenprodil as a lead for further testing in an *in vivo* mouse model of H5N1 infection. The H5N1 is a highly lethal infection in humans with a >50% mortality rate, far larger than the estimated overall mortality rate of COVID-19 disease at <5%.

Notably, treatment with ifenprodil was able to significantly increase the survival of H5N1-infected mice: after 6 days, survival was 60% in the treatment group vs. 0% in the control group, and after 14 days, survival was 40% of ifenprodil-treated animals (see figure inline; No.42 refers to ifenprodil). In addition, several markers of lung function improved significantly including the lung injury score, the lung wet/dry ratio and the infiltrating cell count, in particular T cells and neutrophils. Multiple proinflammatory cytokines/chemokines which are elevated in the “cytokine storm” associated with viral infection were also significantly reduced.

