### 5.1 Inclusion Criteria

1. Male and female subjects aged  $\geq 18$  years of age
2. Confirmed coronavirus infection
  - a) Positive real-time fluorescence polymerase chain reaction of the patient's respiratory or blood specimens for SARS-CoV-2 nucleic acid
  - b) Viral gene sequences in respiratory or blood specimens that are highly homologous to SARS-CoV-2
  - c) Any other diagnostic test accepted by local regulatory authorities
3. Must be hospitalized and requiring supplemental oxygen, or on non-invasive ventilation or high flow oxygen devices (Score of 4 or 5 on WHO Ordinal Clinical Scale)
4. Female subjects of childbearing potential who are sexually active with a non-sterilized male partner must use at least 1 highly effective method of contraception (e.g. oral contraceptives, intrauterine device, diaphragm plus spermicide) from the time of screening and must agree to continue using such precautions for 90 days after the final dose of study drug(s)

5. Non-sterilized males who are sexually active with a female partner of childbearing potential must use condom plus spermicide from day 1 through 90 days after receipt of the last dose of study drug(s)
6. Subjects (or legal designate) must have the capacity to understand, sign and date a written, informed consent form and any required authorization prior to initiation of any study procedures

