## 7.3 Visits

### 7.3.1 Visit 1 (Screening/Baseline/Enrollment)

At Visit 1, information will be collected for evaluation of trial eligibility by provided information as follows and patients will be randomized and dosed after confirmation of eligibility:

- Signing ICF (prior to any trial-related activities)
- Inclusion criteria and exclusion criteria
- Demographics (gender, date of birth, race and ethnic origin) and relevant medical and surgical history
- Confirmation of COVID-19 diagnosis (SARS-CoV-2 RNA confirmation). Include dates of onset of symptoms (if available) and initiation of treatment.
- Pregnancy test (females of reproductive age; Romania: Serum beta-human chorionic gonadotropin [ $\beta$ -HCG]; Rest of World: Serum beta-human chorionic gonadotropin [ $\beta$ -HCG] or urine test is acceptable)
- Vital signs measurements (including pulse, respiration rate, body temperature, systolic and diastolic blood pressure measured with the patient in a seated position [if possible] after  $\geq 3$  minutes of rest), and SpO2. Body weight and height will be included for the screening visit only
- Limited Physical Exam
- Assess baseline measures of clinical support
  - Hospitalized
  - Oxygen requirement
  - Non-invasive mechanical ventilation (via mask)
  - Mechanical ventilator requirement (via endotracheal tube or tracheostomy tube)
  - ECMO requirement
  - Ordinal Scale Assessment
    1. Not hospitalized, no limitations on activities
    2. Not hospitalized, limitation on activities
    3. Hospitalized, not requiring supplemental oxygen
    4. Hospitalized, requiring supplemental oxygen
    5. Hospitalized, on non-invasive ventilation or high flow oxygen devices
    6. Hospitalized, on invasive mechanical ventilation or ECMO
    7. Death
  - For the purposes of eligibility/baseline the worse score from the previous day (Day -1) will be used
  - NEW Score
- Safety laboratory testing
- Child-Pugh Score
- Cytokine Markers
- PaO2 and PaO2/FiO2 ratio
- ECG
- VAS (if possible)
- Extent of Dyspnea (if possible). For the first questionnaire (at baseline), the patient compares their current shortness of breath to their shortness of breath when they are well.)
- Concomitant medications documented
- Randomization\* after eligibility confirmation. All screening/baseline procedures must be completed prior to randomization and administration of study medication.

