##### **7.4.10.1 PaO2 and PaO2/FiO2 Measurement Considerations**

It is recognized that the performing of PaO2 and PaO2/FiO2 measurements can cause significant discomfort to patients. All efforts should be made in obtaining each PaO2 sample as per protocol. However, if not possible (e.g. patient refuses) at a minimum complete PaO2 measurements at baseline, Days 3, 5, 8, 11, 15 and 29.

For those days where PaO2 measurements are not able to be taken, SpO2 should be obtained. First preference is for these measurements to be taken using a forehead sensor. Fingertip probes may be used if forehead sensors are not available. The site should remain consistent with the

method of testing for the patient over the course of the study, e.g. all SpO2 measurements are taken with only forehead sensors.

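### SAP 11.7.3 counts a PaO₂ of 80-100 mmHg as a return whatever oxygen the patient is breathing, so the event mixes oxygen titration with lung recovery

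*SAP*

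**What the plan says.** SAP 11.7 (secondary oxygenation analyses) contains three consecutive time-to-event definitions:

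- 11.7.2: "Date of first return to SpO₂>94% on room air".
- 11.7.3: "Date of first return to PaO₂ of 80-100 mmHg".
- 11.7.4: "Date of first return to PaO₂/FiO₂ of > 400 mmHg".

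The first fixes inspired oxygen and the third divides by it. The second does neither, and it does not require the value to be sustained. Each treats death as a competing risk. Under SAP 11.3 each therefore gets a Fine-Gray hazard ratio against SOC, adjusted for age and site, with a 95% CI and p-value.

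Protocol 5.1 sets the population: "Must be hospitalized and requiring supplemental oxygen, or on non-invasive ventilation or high flow oxygen devices". The entry score is not necessarily the status when the baseline gas is drawn: "For the purposes of eligibility/baseline the worse score from the previous day (Day -1) will be used" (protocol 7.3.1).

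On sampling, protocol 7.4.10.1 asks sites that cannot obtain every gas to do the following: "at a minimum complete PaO 2 measurements at baseline, Days 3, 5, 8, 11, 15 and 29". Neither that section nor footnote j of the schedule (protocol Table 3, SAP Table 1) tells sites to sample on room air.

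SAP 11.3 also says that a time-to-event endpoint is not evaluated if any patient in any arm had the event before randomization. Protocol 7.3.1 places all baseline procedures before randomization.

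**The concern.** PaO₂ depends on both the lung and the oxygen supplied. In patients who enter on oxygen support, raising FiO₂ can bring PaO₂ into the 80-100 mmHg window with no change in the lung. Under 11.7.3 that gas counts the same as one from a patient weaned to room air. The 100 mmHg ceiling works the other way: a patient whose PaO₂ is above 100 mmHg on oxygen has no event until the value falls into the window.

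Phase 2b is open label (protocol 4.4), so oxygen management could differ between arms for reasons other than lung function. The resulting hazard ratio would be hard to interpret. Protocol 4.1 says that Phase 2b data will be used to select and rank secondary endpoints for Phase 3, so an uninterpretable oxygenation result could carry some weight there.

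**Working it through.** The plan gives no event count, power or sample size for this endpoint, so there is no stated figure to reproduce. The check is arithmetic on the SAP's own thresholds.

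**Inputs.** PaO₂ window 80-100 mmHg (SAP 11.7.3). Ratio threshold above 400 mmHg (SAP 11.7.4). The documents do not give FiO₂ on treatment, so the range 0.21 to 1.0 is examined as an assumption.

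**Formulas.** Ratio at the window limits = 80/FiO₂ and 100/FiO₂. PaO₂ that must be exceeded for a ratio above 400 = 400 × FiO₂.

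| FiO₂ | Ratio at PaO₂ 80 | Ratio at PaO₂ 100 | PaO₂ to exceed for ratio > 400 |
|---|---|---|---|
| 0.21 (room air) | 381 | 476 | 84 |
| 0.24 | 333 | 417 | 96 |
| 0.25 | 320 | 400 | 100 |
| 0.30 | 267 | 333 | 120 |
| 0.40 | 200 | 250 | 160 |
| 0.50 | 160 | 200 | 200 |
| 0.60 | 133 | 167 | 240 |
| 1.00 | 80 | 100 | 400 |

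**Crossover.** 100/400 = 0.25. At FiO₂ 0.25 or more, no PaO₂ in the window gives a ratio above 400. Conversely, a ratio above 400 then needs a PaO₂ above 100, outside the window. On any one gas at those settings, the 11.7.3 and 11.7.4 events exclude each other. For example, PaO₂ 90 on FiO₂ 0.5 gives 90/0.5 = 180, which is an event in 11.7.3 only. PaO₂ 110 on FiO₂ 0.25 gives 110/0.25 = 440, which is an event in 11.7.4 only.

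**Against the protocol's own severity marker.** Protocol 2.2 describes acute lung injury and "its severe stage (oxygen index <200) known as acute respiratory distress syndrome (ARDS"). Reading that index as PaO₂/FiO₂, which is an assumption, the lower end of the window falls below 200 once FiO₂ exceeds 80/200 = 0.40. The whole window does so once FiO₂ exceeds 100/200 = 0.50.

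**Interaction with SAP 11.3.** Suppose a baseline PaO₂ of 80-100 mmHg on oxygen counts as an event before randomization. One such patient then removes the analysis. The documents give no rate. If a proportion p of 150 patients had such a gas, independently, the chance of at least one is 1 − (1 − p)^150: 78% for p = 1%, 95% for p = 2%, and over 99% for p = 5%. If *return* instead presupposes an earlier value outside the window, 11.3 is not triggered by such a gas, but the SAP does not say so and leaves in-range baselines undefined.

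**Raw PaO₂ in SAP 11.7.1.** The percentage-change comparison has the same dependence on FiO₂. PaO₂ 120 on FiO₂ 0.6 moving to 85 on room air gives 85/120 − 1 = −29%. Over the same change the ratio goes from 120/0.6 = 200 to 85/0.21 = 405, about double.

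**With a room-air condition.** At FiO₂ 0.21, a PaO₂ of at least 80 and a ratio above 400 (PaO₂ above 84) classify differently only for PaO₂ from 80 to 84.

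**The case against.** The strongest reply is that 11.7.3 matters little. It is in neither secondary endpoint list (protocol 3.2, SAP 2.3.2) nor the interim outputs (SAP 14.1), and SAP 11.1 calls the pilot phase essentially exploratory. The adjacent endpoints 11.7.2 and 11.7.4 account for inspired oxygen and remain. This stands and limits the importance of the point.

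Four stronger readings are tempting but are not supported:

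- **That 11.7.3 contradicts 11.7.4.** All three endpoints can be carried out as written. The conflict is in how one blood gas is classified.
- **That the stated oxygenation objective goes unanswered.** That objective is the rate of change of PaO₂ and PaO₂/FiO₂. It is analysed in 11.7.1, which reports both.
- **That the hazard ratio favours the more heavily supported arm.** More oxygen can bring a low PaO₂ into the window sooner, but it can also push PaO₂ above 100 mmHg and delay the event. The documents contain no FiO₂ data and describe support as assessed and recorded daily, not how it is titrated.
- **That every patient is misclassified.** Oxygen support is required at entry, on the worst score of Day -1. Patients later weaned to room air will have genuine events. The definition cannot separate them from the others.

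SAP 11.3 might be offered as protection, since the analysis is dropped if events precede randomization. It does not repair the definition: under either reading of *return*, changes in oxygen after baseline still count.

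**Conclusion.** The point holds for SAP 11.7.3. The definition lacks an FiO₂ condition, no other section supplies one, and the population enters on oxygen support. As written, the event treats gases with a PaO₂/FiO₂ anywhere from 80 to 476 as the same recovery, across FiO₂ 1.0 to 0.21. At FiO₂ 0.25 or more it cannot agree with 11.7.4 on the same gas.

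The number of patients affected and the direction of any bias cannot be derived from the documents. The 11.3 consequence depends on whether an in-range baseline gas counts as an event, which the SAP leaves open. The ARDS comparison depends on reading the oxygen index as PaO₂/FiO₂. The effect is confined to a supplementary secondary analysis, so this should be corrected but does not threaten the trial's main conclusion.

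**What to change.** In SAP 11.7.3, define the event as the first post-baseline PaO₂ of at least 80 mmHg in a sample taken on room air (FiO₂ 0.21). State openly that the 100 mmHg upper bound is dropped, and that a baseline gas is not an event for the purposes of 11.3. Alternatively, delete 11.7.3 and rely on 11.7.2 and 11.7.4.

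In SAP 11.7.1, keep the planned tests of both PaO₂ and PaO₂/FiO₂, show the FiO₂ in use beside raw PaO₂, and base interpretation on the ratio. Raw PaO₂ should not be reduced to description only: its rate of change is a listed secondary endpoint, and protocol 10.9.2 requires a two-sided test for all secondary efficacy analyses.

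The cost is SAP wording and some programming. The ratio is already collected, so FiO₂ can be recovered as PaO₂ divided by the ratio where it is not recorded separately. The real downside is fewer events. Protocol 7.4.10.1 accepts that gases are uncomfortable and may be refused, with SpO₂ taken instead, and after discharge only the Day 15 and Day 29 measurements remain. If room-air gases prove too sparse, deletion loses little.

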11.8 Secondary Efficacy Analysis: Hospitalization and ICU

11.8.1 Duration of Hospitalization and ICU

Counts and percentages of patients with the following durations for hospitalization and ICU will be reported separately for each treatment arm. The duration calculation is only applicable to patient with the respective hospital or ICU stay. For patients with ongoing hospital or ICU stay with no end date at data cut off, the date of data cut off will be used to calculate the end date for the ongoing at time of data cut off category.

The duration for hospital/ICU stay (Day) is defined as:

Date at hospital discharge-Date of hospital admission+1.

Date at ICU discharge-Date of ICU admission+1.

- < 1 Day
- ≥ 1 Day but < 3 Days
- ≥ 3 Days but < 7 Days
- ≥ 7 Days but < 10 Days
- ≥ 7 Days but < 14 Days
- ≥ 10 Days but < 14 Days
- ≥ 14 Days but < 21 Days
- > 21 Days
- Ongoing at time of data cut off (≥ 1 Day) [The day can be amended based on real data]
- Ongoing at time of data cut off (≥ 3 Days) [The day can be amended based on real data]
- Ongoing at time of data cut off (≥ XX Days) etc...

11.8.2 Time to Hospitalization and ICU discharge

The time to discharge is defined as:

Date of discharge from hospital – Date of Baseline Assessment + 1. (For hospitalization)

Date of discharge from ICU – Date of Baseline Assessment + 1. (For ICU)

If the patient did not discharge from hospital or ICU patient will be censored at the last known date the patient is known to be still in hospital/ICU according to the following:

Final Date of Confirmation the patient is still in hospital - Date of Baseline Assessment + 1. (For hospitalization)

Final Date of Confirmation the patient is still in ICU - Date of Baseline Assessment + 1. (For ICU)

If a patient died discharge, the patient will be censored as a competing risk based on the following:

Date of Death - Date of Baseline Assessment + 1.

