2.3.2 Secondary endpoints

- Status on an ordinal scale assessed daily while hospitalized and on days 15 and 28 in IP versus control group patients
- NEWS assessed days 3, 5, 8, 11 while hospitalized and on days 15 and 29 in IP versus control group patients
- Rate of mechanical ventilation in IP versus control group patients
- Duration of mechanical ventilation (if applicable) in IP versus control group patients
- Duration of supplemental oxygen in IP versus control group patients
- Time to return to SpO₂ > 94% on room air
- Duration in ICU (if applicable) in IP versus control group patients
- Rate of Mortality in IP versus control group patients
- Duration of hospitalization in IP versus control group patients
- Time to discharge in IP versus control group patients
- Effect on the rate of change of partial pressure of oxygen (PaO₂) and PaO₂/FiO₂ ratio taken at baseline and measured once daily up to 2 weeks of treatment in IP versus control group patients

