11.2 Secondary Efficacy Analysis: General Population Considerations

All secondary efficacy analyses will be performed for ITT and PPS.

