11.3 Secondary Efficacy Analysis: Time to Event General Considerations

Time to event endpoints will not be evaluated if any subjects experienced an event prior to randomization in any of the treatment arms.

Time-to-event endpoints without competing risk will be analysed for each dosing group using the Kaplan-Meier (KM) method. Medians (with corresponding 95% confidence intervals) and quartiles (25th and 75th percentiles), minimum, and maximum survival times will be presented. In addition, the number of patients with an event and the number of censored patients will also be reported. The corresponding Kaplan-Meier survival plot will also be presented along with number at risk statistics at the appropriate time points. Adjusted hazard ratio, 95% CIs and p-values between active treatment groups to SOC under Cox proportional hazard model with age, site and treatment groups as covariates will be reported.

Time-to-event endpoints with competing risk will be analysed for each dosing group using the Cumulative Incidence Function-CIF (KM) graphical display. Adjusted hazard ratio, 95% CIs and p-values between active treatment groups to SOC under Fine-Gray sub-distribution hazard model with age, site and treatment groups as covariates will be reported. Competing risk is identified by the presence of death outcome, which prevent the observation of the current outcome of interest.

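### Time to ICU discharge is counted from baseline with no rule for patients never in the ICU, so later ICU entry reads as slower discharge in the only ICU result the SAP tests

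*SAP*

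**What the plan says.** SAP 11.8.2 starts the clock at baseline for both hospital and ICU discharge. For the ICU, the event time is "Date of discharge from ICU – Date of Baseline Assessment + 1. (For ICU"). A patient not yet discharged is censored at "Final Date of Confirmation the patient is still in ICU - Date of Baseline Assessment + 1. (For ICU"), and death is a competing risk. No date is defined for a survivor who was never in the ICU.

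SAP 11.3 sets the model for endpoints with a competing risk: "Adjusted hazard ratio, 95% CIs and p-values between active treatment groups to SOC under Fine-Gray sub-distribution hazard model", with age, site and treatment as covariates. On population, SAP 11.2 says only "All secondary efficacy analyses will be performed for ITT and PPS".

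The ICU stay is handled separately. SAP 2.3.2 lists "Duration in ICU (if applicable) in IP versus control group patients" as a secondary endpoint, and SAP 11.8.1 measures it as "Date at ICU discharge-Date of ICU admission+1". There, "The duration calculation is only applicable to patient with the respective hospital or ICU stay", and the output is descriptive: "Counts and percentages of patients with the following durations for hospitalization and ICU will be reported separately for each treatment arm". No test or interval is specified for it.

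Protocol 10.9.2 names ICU discharge among the events for Kaplan-Meier summary and proportional hazards regression, and tests secondary analyses two-sided at 5%. Protocol 5.1 and 5.2 admit patients at WHO score 4 or 5 and exclude mechanical ventilation. ICU status is not an entry criterion.

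**The concern.** A patient cannot be discharged from the ICU before being admitted to it. With a baseline origin, the days before admission still count as time to ICU discharge. An arm whose patients enter the ICU later therefore accumulates longer times, and its hazard ratio for discharge falls below 1, although later entry is no disadvantage to the patient.

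Patients never in the ICU are a second problem. If they drop out because they have no date, the arms are compared within a group selected by an event after randomization. If they stay in as never discharged, preventing admission lowers the discharge hazard. Either way, a favourable effect can appear with the wrong sign.

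This matters because Phase 2b data are to be used to select and rank the secondary endpoints for Phase 3 (protocol 4.1, SAP 2.1).

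**Working it through.** The documents state no figure for ICU discharge, so there is nothing of the plan's own to reproduce. They also give no ICU admission rate, entry time or length of stay. Those inputs below are assumptions, and they are varied.

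**1. The two SAP definitions are linked by an identity.**

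Time by 11.8.2 = discharge − baseline + 1 = (admission − baseline) + (discharge − admission + 1) = entry delay + duration by 11.8.1.

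Two patients with the same stay, baseline on Day 1:

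| ICU entry | ICU discharge | Entry delay | Duration (11.8.1) | Time (11.8.2) |
|---|---|---|---|---|
| Day 3 | Day 10 | 2 | 8 | 10 |
| Day 6 | Day 13 | 5 | 8 | 13 |

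The stay is equal. The measured time differs by exactly the 3 days of later entry.

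**2. Effect on medians, ICU patients only.** Assumed: stay follows a gamma distribution (shape 2, scale 3 days, median 5.0) in both arms. Entry delay is exponential with mean 2 days in SOC and 3 or 5 days in the active arm, and zero for patients already in the ICU at baseline. No deaths. Time = delay + stay + 1.

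| In ICU at baseline | SOC median | Active, mean delay 3 | Gap | Active, mean delay 5 | Gap |
|---|---|---|---|---|---|
| None | 8.10 | 9.02 | 0.9 | 10.70 | 2.6 |
| Half | 7.06 | 7.47 | 0.4 | 8.11 | 1.1 |
| 80% | 6.43 | 6.56 | 0.1 | 6.75 | 0.3 |

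The true difference in stay is zero in every row.

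**3. Effect on the hazard ratio, ICU patients only.** Other assumed inputs: stay gamma with mean 8 days in both arms, SOC entry at about Day 4, active entry later by a fixed number of days. Unadjusted Cox model, no deaths, 400 simulated trials per setting.

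| ICU patients per arm | 1 day later | 2 days | 3 days | 5 days |
|---|---|---|---|---|
| 10 | 0.86 | 0.72 | 0.62 | 0.39 |
| 15 | 0.84 | 0.72 | 0.63 | 0.47 |
| 50 | 0.87 | 0.77 | 0.66 | 0.50 |

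At a 3-day delay, a nominally significant result against the drug (p<0.05) occurs in about 16%, 22% and 50% of trials for 10, 15 and 50 ICU patients per arm. Fifty is the ceiling, since it needs every patient in a 50-patient arm to reach the ICU. With half already in the ICU at baseline (50 per arm), delays of 2, 3 and 5 days give 0.86, 0.80 and 0.67. Counted from ICU admission, the hazard ratio is 0.98 to 1.05 in every setting.

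**4. If never-ICU patients are kept as never discharged.** Assume the same entry timing and stay in both arms, no deaths, and all ICU patients discharged by Day 29. The cumulative incidence of ICU discharge then ends at the admission proportion p, and the ratio of cumulative subdistribution hazards is ln(1 − p active) / ln(1 − p SOC).

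- Admission 30% SOC, 20% active: ln(0.80)/ln(0.70) = 0.223/0.357 = 0.63.
- Admission 40% SOC, 20% active: ln(0.80)/ln(0.60) = 0.223/0.511 = 0.44.

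Simulation of the same two cases gave 0.66 and 0.45. Fewer admissions read as slower discharge.

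**The case against.** The strongest reply is that the ICU stay is already measured from admission in SAP 11.8.1, so a reader of the report would see unchanged durations beside any shifted time to discharge. That stands. A reader might infer that the plan makes the drug appear to prolong the ICU stay, or that the listed ICU-duration endpoint is biased. The documents do not support this, because 11.8.1 analyses that endpoint without the distortion. It does not rescue 11.8.2, which carries the only ICU hazard ratio and p-value.

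A reader might also take 11.8.2 to be limited to patients who reach the ICU. That sentence belongs to the duration calculation in 11.8.1, while 11.2 says ITT and PPS. The accurate statement is that 11.8.2 leaves its risk set undefined. Steps 3 and 4 of the working show that both ways of filling the gap can mislead.

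The 2.6-day gap should not be taken as typical. It needs nobody in the ICU at baseline and a 2.5-fold longer mean delay. Score 5 patients are eligible, so many may already be in the ICU. Nor does SAP 11.3 call for medians where there is a competing risk, so the medians only illustrate size.

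Finally, a baseline origin is the SAP's convention for time-to-event endpoints, the SAP covers only Phase 2b, it calls this phase essentially exploratory, and no decision rule uses this hazard ratio. That limits the consequence. It does not make the estimate interpretable.

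**Conclusion.** The point holds for the time-to-ICU-discharge analysis in SAP 11.8.2. The direction follows from the definition: among ICU patients, entry delay adds day for day. The size is not known from the documents. Under the assumptions in step 2, the spurious gap in medians runs from about 0.1 to 2.6 days, shrinking as more ICU patients are already there at baseline and vanishing if all are. Hazard ratios in step 3 run from 0.39 to 0.87, depending on the delay, the number of ICU patients and the share in the ICU at baseline. All these figures come from models without deaths or covariate adjustment.

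Moving the origin to ICU admission would remove the entry-delay artefact, but the comparison would still be among patients selected after randomization. This is a secondary analysis in a pilot phase. It should be corrected, but it does not affect the primary endpoint.

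**What to change.** In SAP 11.8.2, remove the ICU hazard ratio, interval and p-value. Keep the 11.8.1 description of stay from ICU admission among those admitted, without a test.

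Compare the arms instead on days alive and out of the ICU to Day 29 in all ITT patients: 28 for a survivor never in the ICU, 0 for a patient who dies. Values are likely to pile up at 0 and 28, so use a rank-based or ordinal model adjusted for age and site. State how patients lost before Day 29 are handled. This parallels the ventilator-free-days objective in SAP 2.2.2.

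Record the change in SAP section 13 as a departure from protocol 10.9.2.

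The cost is one new derived variable, built from ICU dates that 11.8.1 already needs, and a documented departure from the protocol for a secondary analysis. What is lost is a hazard ratio that cannot be interpreted as it is now defined.
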